5.11.1.1 Adverse Events

The number and percentage of patients experiencing at least 1 treatment emergent adverse event will be tabulated by MedDRA primary system organ class, high level term, preferred term, and treatment group. For the number of patients with AEs, patients reporting the same event more than once will have that event counted only once within each body system, once within each high level term, and once within each preferred term. AEs will be coded using the MedDRA dictionary.

The number and percentage of patients experiencing at least 1 treatment emergent AE considered related to treatment will also be summarized. If the event is missing relationship data, the event will be included in the total column for the corresponding treatment group. Multiple occurrences of the same event are counted once per subject using the most related event.

AEs will also be summarized by intensity grade. Again, multiple occurrences of the same event are counted once per subject using the maximum intensity. If the intensity of an AE is missing, the event will be included in the total column for the corresponding treatment group.

The following tabulations will also be presented:

- Incidence of treatment-emergent adverse events by System Organ Class (SOC), high-level term, and preferred term

Brentuximab vedotin (ADCETRIS™)
Statistical Analysis Plan, Study C25003

- Incidence of treatment-emergent adverse events reported by at least 10% of patients in either treatment group by MedDRA preferred term
- Incidence of treatment-emergent adverse events considered by the investigator to be related to study drug by MedDRA SOC, high-level term and preferred term
- Incidence of treatment-emergent adverse events that caused study drug dose modification by MedDRA SOC, high-level term and preferred term

For treatment-emergent adverse events with NCI CTCAE toxicity Grade 3 or higher, the following summaries are to be produced:

- Incidence of Grade ≥ 3 treatment-emergent adverse events, by SOC, high-level term and preferred term
- Incidence of Grade ≥ 3 treatment-emergent adverse events considered by the investigator to be related to study drug, by SOC, high-level term and preferred term

5.11.1.2 Serious Adverse Events

The number and percentage of patients experiencing at least 1 treatment-emergent serious AE (SAE) will be summarized by MedDRA primary system organ class, high-level term, and preferred term. The following summaries are to be produced:

- Incidence of treatment-emergent serious adverse events, by SOC, high-level term and preferred term
- Incidence of treatment-emergent serious adverse events considered by the investigator to be related to study drug, by SOC, high-level term and preferred term

In addition, a by-subject listing of the SAEs will be presented (the subject listing will contain all SAEs regardless of treatment emergent AE status).

5.11.1.3 Deaths

All deaths occurring on-study and during follow-up will be summarized. Cause of death will be summarized as well in this table. Frequencies of deaths due to study treatment-related adverse events will also be reported.

Brentuximab vedotin (ADCETRIS™)
Statistical Analysis Plan, Study C25003

A by-subject listing of the deaths will be presented. All deaths occurring on-study and during follow-up will be displayed (regardless of treatment emergent AE status).

5.11.1.4 Adverse Events Resulting in Discontinuation of Study Drug

Adverse events results in discontinuation of study drug will be tabulated by treatment. A by-subject listing of AEs resulting in discontinuation of study drug will be presented.

5.11.2 Laboratory Data

For the purposes of summarization in both the tables and listings, all laboratory values will be converted to standardized units. If a lab value is reported using a non-numeric qualifier (eg, less than (<) a certain value, or greater than (>) a certain value), the given numeric value will be used in the summary statistics, ignoring the non-numeric qualifier. In case a central lab value is missing, the local lab, if available, will be used.

If a subject has repeated laboratory values for a given time point, the value from the last evaluation will be used.

The parameters to be analyzed are as follows:

- Hematology: hemoglobin, hematocrit, platelet count, leukocytes with differential, neutrophils (absolute neutrophil count [ANC])
- Serum chemistry: Blood urea nitrogen, Creatinine, Total bilirubin, Urate, Lactate dehydrogenase, Gamma-glutamyl transpeptidase (GGT), Phosphate, Albumin, Alkaline phosphatase (ALP), AST, ALT, Glucose, Sodium, Potassium, Calcium, Chloride, Carbon dioxide, Magnesium.
- Other: Hemoglobin A1C

Laboratory data of hematology and clinical chemistry up to 30 days after last dose or the End of Treatment visit date, whichever is later, will be reported in SI units. Normal ranges from the central and local laboratories used in this study will be listed.

Summary statistics (mean, standard deviation, median, and range) will be calculated for the raw data and for their percentage changes from baseline at each time point of assessment and for the percentage changes from baseline to the last value. Individual values outside the

**Brentuximab vedotin (ADCETRIS™)
Statistical Analysis Plan, Study C25003**

normal ranges will be identified (by “H” for high and “L” for low) in the data listings displaying the absolute values for each subject.

Shift tables from baseline to worst value (ie, worst grade) on study (from treatment start to 30 days after last dose or the End of Treatment visit date, whichever is later) will be provided for the following laboratory parameters: hemoglobin, ANC, WBC, platelets, AST, ALT, bilirubin and HbA1C.

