**Brentuximab vedotin (ADCETRIS®)**

**Clinical Study Protocol C25003 Amendment 7, EudraCT: 2011-005450-60**

have experienced a prior infusion-related reaction should be premedicated according to institutional guidelines for subsequent infusions. Premedication may include acetaminophen, an antihistamine and a corticosteroid.

Clinically significant laboratory abnormalities were to be reported as adverse events per the phase 2 study protocols. Central laboratory data were collected only predose for each treatment cycle. Few patients overall had postbaseline worsening to Grade 3 or higher in clinical laboratory values. The clinical laboratory parameters for which the most patients had new or worsening shifts to  $\geq$ Grade 3 were low neutrophils (11%), lymphocytes (11%), platelets (6%), leukocytes (5%), and high glucose (6%). Only 1 patient in the phase 2 studies had Grade 3 ALT and AST.

Any treatment that can decrease immune function may contribute to malignancy and infections; patients are to be monitored for these events during the treatment period and up to and including 30 days after the last dose of frontline therapy.

Complete blood counts should be monitored prior to each dose of brentuximab vedotin and more frequent monitoring should be considered for patients with Grade 3 or 4 neutropenia. Prolonged ( $\geq$ 1 week) severe neutropenia can occur. If Grade 3 or 4 neutropenia develops, manage by dose delays, reductions, or discontinuations (see [Table 6-1](#)).

Tumor lysis syndrome may occur. Patients with rapidly proliferating tumor and high tumor burden are at risk of tumor lysis syndrome and should be closely monitored. If tumor lysis syndrome occurs, take medically appropriate measures.

Stevens-Johnson syndrome has been reported with brentuximab vedotin. If Stevens-Johnson syndrome occurs, brentuximab vedotin must be discontinued and the appropriate medical therapy administered.

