#### **7.4.12 Clinical Laboratory Evaluations**

Clinical laboratory evaluations will be performed centrally. Decisions regarding eligibility for this study may be made using local laboratory determinations. For dosing decisions, local hematology and chemistry laboratory results may be used.

Handling and shipment of clinical laboratory samples will be outlined in the Study Manual.

Clinical laboratory evaluations will be performed as outlined below.

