**Brentuximab vedotin (ADCETRIS®)**

**Clinical Study Protocol C25003 Amendment 7, EudraCT: 2011-005450-60**

- Treatment-emergent AEs
- Drug-related treatment-emergent AEs
- Grade 3 or higher treatment-emergent AEs
- Grade 3 or higher drug-related treatment-emergent AEs
- The most commonly reported treatment-emergent AEs (ie, those events reported by  $\geq 10\%$  of all patients)
- SAEs

A listing of treatment-emergent AEs resulting in frontline therapy discontinuation will be provided.

Descriptive statistics for the actual values of clinical laboratory parameters (and/or change from baseline in clinical laboratory parameters) will be presented for all scheduled measurements over time. Mean laboratory values over time will be plotted for key laboratory parameters.

Descriptive statistics for the actual values (and/or the changes from baseline) of vital signs and weight over time will be tabulated by scheduled time point.

Shift tables for laboratory parameters will be generated based on changes in NCI CTCAE grade from baseline to the worst postbaseline value. Graphical displays of key safety parameters, such as scatter plots of baseline versus worst postbaseline values, may be used to understand the safety profile of patients' frontline therapies.

All concomitant medications collected from screening through the study period will be classified to preferred terms according to the World Health Organization (WHO) drug dictionary.

Additional safety analyses may be performed to most clearly enumerate rates of toxicities and to further define the safety profile of patients' frontline therapies.

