6. CHANGES TO PLANNED ANALYSES FROM PROTOCOL

Not applicable

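### SAP 5.11.2 does not say whether its last-repeat and central-first laboratory rules apply before the worst grade is taken, so the shift tables could miss the worst value

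*SAP*

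**What the plan says.** Three statements in SAP 5.11.2 bear on this point:

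- Repeats: "If a subject has repeated laboratory values for a given time point, the value from the last evaluation will be used".
- Laboratory source: "In case a central lab value is missing, the local lab, if available, will be used".
- Shift tables: "Shift tables from baseline to worst value (ie, worst grade) on study". The window runs from the start of treatment to the later of 30 days past the last dose and the EOT visit. The parameters are hemoglobin, ANC, WBC, platelets, AST, ALT, bilirubin and HbA1C.

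Protocol 8.1.9 specifies the same kind of table: "Shift tables for laboratory parameters will be generated based on changes in NCI CTCAE grade from baseline to the worst postbaseline value". SAP Section 6, on changes from the protocol, reads "Not applicable".

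Four other places matter. SAP 5.4.3 assigns data to visits by the eCRF visit designator and gives no rule for unscheduled laboratory values. SAP 5.4.2 puts the central laboratory ahead of the local one for baseline, even when the local sample is more recent. SAP 5.11.3 says outright that unscheduled and retested ECGs are included; 5.11.2 has no matching words for laboratory data. Protocol 7.4.12 makes central testing the standard but adds: "For dosing decisions, local hematology and chemistry laboratory results may be used".

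**The concern.** A shift table should show the worst grade each patient reached. A last-value rule works against that when the repeat was ordered because the first value was bad. A low predose count is a likely reason for a retest, and the retest will often be the better of the two. If the rule thins the data first, the worst grade is taken over records from which some of the worst values have already gone.

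Local results raise a related question. They may be used for dosing decisions, so a local and a central value can exist for the same visit. If the central value displaces the local one, the result behind a treatment decision may not reach the shift table.

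The adverse event tables cover this only in part. Under Protocol 10.1.2 an abnormal laboratory value becomes an AE only if it leads to an action on treatment or an intervention, or the investigator judges it a clinically significant change. The shift tables are the graded laboratory summary that the plan commits to without that filter. Neutropenia is common with this regimen: Protocol 1.3 reports Grade 3 or higher neutropenia in 17 of 26 phase 1 patients on brentuximab vedotin plus AVD.

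**Working it through.** The plan attaches no figure to this point, so there is none to reproduce. The check is first textual, then an illustration of size.

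**Two readings of SAP 5.11.2**

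Take a hypothetical patient whose ANC at one visit is Grade 4, with a repeat entered under the same visit at Grade 2, and no other value worse than Grade 2.

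- Reading A, select then take the worst: the repeat rule keeps Grade 2 for that visit, and the shift table shows Grade 2.
- Reading B, worst of all values: the shift table shows Grade 4.

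Reading B agrees with the shift-table sentence and with Protocol 8.1.9. Reading A follows the repeat rule as written, which has no exception. The SAP does not choose between them, so two competent programmers could report different grades from the same data.

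**Direction**

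The last-repeat rule tends towards the milder grade where bad values prompt the repeats. The central-first rule has no fixed direction: it loses a low local value beside a higher central one, but keeps a low central value beside a higher local one.

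**Illustration of size under Reading A, last-repeat rule only**

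Input from the documents: p = 17/26 = 65.4% with Grade 3 or higher neutropenia (Protocol 1.3). This is a phase 1 adverse event rate, used as a stand-in for a laboratory rate.

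Assumption: f is the share of those patients whose only Grade 3 or higher readings are superseded by a milder repeat. Tabulated rate = p × (1 − f).

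| f | Tabulated rate |
|---|---|
| 0 | 65.4% |
| 2% | 64.1% |
| 5% | 62.1% |
| 10% | 58.8% |
| 20% | 52.3% |
| 30% | 45.8% |

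To see what could produce such values of f, model the visits. The Schedule of Events has predose samples on Days 1 and 15 of six cycles plus EOT. Cycle 1 Day 1 serves as baseline, which leaves 11 + 1 = 12 post-baseline time points. With independent visits, the per-visit probability v solves 1 − (1 − v)^12 = 17/26, so v = 1 − (9/26)^(1/12) = 0.0846. Let r be the assumed chance that a Grade 3 or higher value is repeated under the same visit, and c the assumed chance that the repeat is below Grade 3. Then:

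Tabulated rate = 1 − (1 − v(1 − rc))^12

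The last column comes from a simulation in which risk varies between patients (beta distribution, shape parameters summing to 2, mean set to give the same 65.4%).

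| r | c | Independent visits | Patients differ in risk |
|---|---|---|---|
| 10% | 50% | 63% | 65% |
| 30% | 50% | 59% | 63% |
| 60% | 90% | 38% | 52% |

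Under Reading B every entry is 65.4%. The values of f, r and c are all assumptions; the documents give none of them.

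**Parameter list**

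Protocol 1.5 names five parameters with the most new or worsening shifts to Grade 3 or higher in the phase 2 studies: neutrophils 11%, lymphocytes 11%, platelets 6%, glucose 6% and leukocytes 5%. Lymphocytes and glucose are not on the SAP's shift list. Both are sampled predose at every dosing visit. HbA1C is on the list, but is measured only at screening and EOT.

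**The case against.** The strongest reply is that there is no conflict. The repeat rule speaks of a given time point, which matches the by-time-point summary statistics. The shift-table sentence has its own definition over the whole on-study window, and a specific definition can be read as overriding a general rule. On that reading nothing is lost. This stands as a possible reading, but the SAP does not say it, and 5.11.3 shows that its authors wrote out the inclusion of retests where they had it in mind.

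Several stronger claims are tempting, and the documents do not support them:

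- A reader might infer that the shift tables will understate toxicity. The text shows only that they could. A later repeat displaces the first value only if it is entered under the same visit, and the SAP does not say that it must be.
- A reader might infer that the rules are expressly stated for all tables and listings. That phrase in 5.11.2 introduces unit conversion only.
- A reader might infer that local results are always discarded when a central one exists. For post-baseline data this is the natural inference but is not written; precedence is explicit only at baseline. Local values with no central counterpart are used.
- A reader might infer a bias between arms, for example because Table 6-1 addresses growth factors for A+AVD. The laboratory rules are the same in both arms, and Protocol 6.4 permits colony stimulating factors for neutropenia without restriction by arm.
- A reader might infer that nothing else would reveal the lost values. Values that led to a delay, dose change or intervention qualify as AEs and enter the Grade 3 or higher tables (SAP 5.11.1.1). SAP 5.11.2 also plans by-time-point statistics and flagged listings, and Protocol 8.1.9 allows scatter plots of worst postbaseline values. Values that met no AE trigger remain outside the AE tables.
- A reader might infer that leaving out lymphocytes and glucose departs from the protocol. Protocol 8.1.9 does not prescribe the shift parameters, the phase 2 percentages come from relapsed disease on a different regimen, and both analytes remain among the parameters to be analysed.

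**Conclusion.** The point holds as an unscoped rule that is ambiguous against the worst-grade definition. Applied literally and first, the last-repeat rule can make the shift tables miss the worst value, contrary to the SAP's own sentence and Protocol 8.1.9, and no change from the protocol is declared. Any error from that rule would tend to understate Grade 3-4 cytopenia, provided that low counts prompt repeats and the repeats share a visit designator. The central-first rule adds uncertainty without a clear direction.

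The size cannot be computed from the documents. It is zero under the overriding reading, and the illustrative figures show only how the loss would grow with assumed rates. No distortion of the comparison between arms is shown. This is a clarification of safety reporting that should be made; it does not touch the primary or other efficacy analyses.

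**What to change.** In SAP 5.11.2:

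1. Limit the last-repeat and central-first rules to the by-time-point summary statistics.
2. State that shift tables use the worst CTCAE grade among all post-baseline values in the window: scheduled, repeat, unscheduled, central and local. Grade each value on its own laboratory's range where the grade depends on that range.
3. Optionally, add lymphocytes and glucose to the shift list, since both are already collected and Protocol 1.5 names them.

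The cost is a few sentences and minor programming. Unit conversion is already planned. Local normal ranges are planned only for listing, so using them for grading is some extra work. No new data collection is needed.

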**Brentuximab vedotin (ADCETRIS®)****Clinical Study Protocol C25003 Amendment 7, EudraCT: 2011-005450-60**

growth factor support in some cases. Infusion-related reactions occurred in approximately 10% of patients and were typically managed by dose interruption. Infusion-related reaction prophylaxis in subsequent treatment cycles was instituted at the discretion of the investigator. The clinical laboratory parameters for which the most patients had new or worsening shifts to  $\geq$ Grade 3 were low neutrophils (11%), lymphocytes (11%), platelets (6%), leukocytes (5%), and high glucose (6%). Only 1 patient in the phase 2 studies had Grade 3 alanine aminotransferase (ALT) and Grade 3 aspartate aminotransferase (AST).

In the phase 2 studies, 31% of patients had an SAE, 28% had a Grade 3 or higher SAE, and 15% had an SAE that was determined by the investigator to be related to brentuximab vedotin. The most common SAE preferred terms (2%) were abdominal pain, disease progression (recurrent sALCL), pulmonary embolism, and septic shock. A higher proportion of patients with sALCL experienced SAEs, including deaths within 30 days of last dose, relative to patients with HL, likely due to the older age and more aggressive nature of the malignancy in this patient population.

A total of 9 deaths were reported within the safety evaluation period (within 30 days of the last dose of brentuximab vedotin) in 357 patients across the six phase 1 and phase 2 studies for which data are available. Two patient deaths (0.6%) were considered related to study treatment. One patient in Study SG035-0001 who received 3.6 mg/kg in phase 1 died due to febrile neutropenia and presumed septic shock. A second treatment-related death in Study SGN35-008A was attributed to pancytopenia, cytomegalovirus (CMV) infection, and intracranial hemorrhage. The remaining on-study deaths were primarily related to disease progression in patients with sALCL.

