## **Brentuximab vedotin (ADCETRIS®)**

### **Clinical Study Protocol C25003 Amendment 7, EudraCT: 2011-005450-60**

The statistical methods are outlined below; analysis details will be provided in the statistical analysis plan (SAP). The SAP will be written by Millennium and will be finalized prior to the formal interim analysis.

Deviations from the statistical analyses outlined in this protocol will be indicated in the SAP; any further modifications will be noted in the final clinical study report.

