#### **10.1.2 Adverse Event Definition**

Adverse event (AE) means any untoward medical occurrence in a patient or subject administered a pharmaceutical product; the untoward medical occurrence does not necessarily have a causal relationship with this treatment. An AE can therefore be any unfavorable and unintended sign (including an abnormal laboratory finding), symptom, or disease temporally associated with the use of a medicinal (investigational) product whether or not it is related to the medicinal product. This includes any newly occurring event, or a previous condition that has increased in severity or frequency since the administration of study drug.

An abnormal laboratory value will not be assessed as an AE unless that value leads to discontinuation or delay in treatment, dose modification, therapeutic intervention, or is considered by the investigator to be a clinically significant change from baseline.

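### The SAP's list of laboratory shift tables leaves out lymphocytes and glucose, so graded by-arm reporting of these two parameters rests on adverse event tables alone

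*SAP*

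**What the plan says.** SAP 5.11.2 provides shift tables from baseline to worst grade, from treatment start to the later of 30 days after last dose and the End of Treatment (EOT) visit. It names eight parameters: the tables "will be provided for the following laboratory parameters: hemoglobin, ANC, WBC, platelets, AST, ALT, bilirubin and HbA1C". The same section's list of parameters to be analyzed is longer. It includes the leukocyte differential and glucose, which receive per-visit summary statistics, percentage changes from baseline and high/low flags in listings.

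Protocol 8.1.9 is general: "Shift tables for laboratory parameters will be generated based on changes in NCI CTCAE grade from baseline to the worst postbaseline value". It names no parameters. It also allows, without requiring, more: "Additional safety analyses may be performed to most clearly enumerate rates of toxicities".

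Protocol 1.3 and 1.5 report the parameters for which most phase 2 patients shifted to Grade 3 or higher: neutrophils (11%), lymphocytes (11%), platelets (6%), leukocytes (5%) and high glucose (6%). Protocol 1.5 adds the context that "Few patients overall had postbaseline worsening to Grade 3 or higher in clinical laboratory values".

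On AEs, protocol 10.1.2 states: "An abnormal laboratory value will not be assessed as an AE unless that value leads to discontinuation or delay in treatment", and then adds dose modification, therapeutic intervention and the investigator's judgment of a clinically significant change. Protocol 10.2 also counts clinically relevant laboratory deterioration. SAP 5.11.1.1 tabulates AEs by intensity grade, with separate tables for Grade 3 or higher.

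**The concern.** The safety profile of A+AVD relative to ABVD is a secondary objective. A worst-grade shift table is the standard way to compare graded laboratory toxicity by arm without depending on whether the investigator reported an AE. Two parameters that the protocol's own background puts among the leading laboratory shifts with brentuximab vedotin have no such table on the SAP list.

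Lymphocytes have some further relevance. Protocol 1.5 warns that reduced immune function may contribute to infections. A low lymphocyte count is also one of the prognostic factors in protocol 15.5, so some patients may enter the trial with lymphopenia. A shift from baseline separates that from worsening on treatment.

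What is at stake is the completeness of a descriptive safety comparison, and nothing beyond that.

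**Working it through.** There is no sample size, power or alpha figure to reproduce. The check compares two lists and then asks whether any other planned output fills the difference.

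**1. The two lists side by side**

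| Named in protocol 1.3 and 1.5 (phase 2 rate) | On the SAP 5.11.2 shift list | In the SAP 5.11.2 analyzed list |
|---|---|---|
| Neutrophils (11%) | Yes, as ANC | Yes |
| Lymphocytes (11%) | No | Yes, through the differential |
| Platelets (6%) | Yes | Yes |
| Leukocytes (5%) | Yes, as WBC | Yes |
| High glucose (6%) | No | Yes |

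Three of five are covered and 5 − 3 = 2 are not: lymphocytes and glucose.

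**2. Whether a listed parameter substitutes**

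- HbA1C for glucose: footnote f of the Schedule of Events places HbA1C at screening and EOT, which is one scheduled postbaseline value. Chemistry, with fasting glucose, is predose on Days 1 and 15 of each cycle and at EOT. Over six cycles that is 6 × 2 = 12 predose samples, less Cycle 1 Day 1 (baseline), plus EOT: 12 − 1 + 1 = 12 postbaseline values. HbA1C gives partial glycemic coverage but not the worst on-treatment glucose grade.
- WBC for lymphocytes: the total count does not isolate lymphocytes.

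**3. Whether another planned output gives worst laboratory grade per patient, by arm**

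- Per-visit summaries and flagged listings do not; they carry no per-patient worst grade.
- AE tables do give grades by arm, but only for values that meet protocol 10.1.2 or 10.2. The values left out are those with no action taken and judged neither clinically significant nor relevant.
- AE and laboratory sources need not agree. In the phase 2 studies (protocol 1.3), Grade 3 and Grade 4 neutropenia occurred in 13% and 7% of patients, while laboratory neutrophil shifts to Grade 3 or higher occurred in 11%. Here the AE figure was the larger, so this shows only that one source does not stand in for the other, not that AEs under-report.

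**4. Whether the number missed can be derived**

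It cannot. The 11% and 6% come from monotherapy at 1.8 mg/kg every 3 weeks in relapsed or refractory disease. The closest regimen data are the 26 brentuximab vedotin plus AVD patients in protocol 1.3, whose Grade 3 or higher events include neither lymphopenia nor hyperglycemia. That list is AE-based and may not be exhaustive. Even read as 0 of 26, the exact two-sided 95% upper limit is 1 − 0.025^(1/26) = 0.132, or 13.2%, so it does not settle the laboratory rate. Neither source says what share of graded values would go unreported as AEs.

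**The case against.** The strongest case against is that the SAP list is a legitimate choice. Protocol 8.1.9 does not promise a shift table for every parameter, and protocol 8.1 leaves analysis details to the SAP. The five-parameter list is background from another population and schedule; it does not designate parameters of special interest for this trial. Coverage is also substantial: both parameters are summarized at each visit, AEs are tabulated at every grade and not only Grade 3 or higher, the AE criteria are broad, and additional safety analyses are allowed.

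Much of this stands. It rules out one inference that a reader might draw: that the SAP departs from the protocol without saying so. Protocol 8.1 does say "Deviations from the statistical analyses outlined in this protocol will be indicated in the SAP", and SAP Section 6 ("CHANGES TO PLANNED ANALYSES FROM PROTOCOL") reads Not applicable. But the SAP list can be read as specifying the general sentence in protocol 8.1.9, so that entry is not shown to be wrong.

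The objection does not remove the narrower point. The SAP list is closed, and as written it excludes two parameters that the protocol puts among the leading shifts. The additional analyses are optional, and none of the planned outputs gives per-patient worst laboratory grade by arm for these two.

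**Conclusion.** The point holds as a minor improvement to descriptive safety reporting. Its size is two of five named parameters without a listed shift table. That 2/5 (40%) describes a list, not a loss of patients or information.

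A reader might multiply the phase 2 rates by the planned arm size (620 × 0.11 = 68.2 and 620 × 0.06 = 37.2) and conclude that dozens of patients per arm would go uncounted. The documents do not support this. Those products assume that relapsed or refractory monotherapy rates apply here and that all 620 are treated, and they count everyone a shift table would show, including patients whose values also appear as AEs. Nor do the documents show that AE capture differs between the arms.

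The conclusion rests on taking the SAP list as exhaustive and on the AE criteria of protocol 10.1.2 and 10.2. It has no bearing on efficacy inference, dosing or stopping.

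**What to change.** In SAP 5.11.2, add lymphocytes (absolute count, low direction) and fasting glucose (high direction) to the parameters with baseline-to-worst-grade shift tables, presented by treatment arm and over the window already stated there. No entry in SAP Section 6 is needed.

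The cost is a short wording change and two more tables. Both parameters are already collected and already in the SAP's analyzed list, so no new assessment or site burden follows.
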